Risks to Health: Potential unanticipated problems require prompt reporting to Aspire IRB. These problems potentially place subjects or others at greater risk of physical or psychological harm than was previously recognized, and warrant consideration of substantive changes in the protocol or informed consent process or other action in order to protect the safety, welfare, or rights of participants. Aspire IRB must be notified within 5 calendar days of the event. The completed IRB Unanticipated Problem form (Appendix 3) must be received by Aspire IRB within 10 calendar days of the event. Unanticipated problems are defined as those problems which alter the risks to subjects or others. This includes any study suspensions or holds. This form will be used to report any problem that is unforeseen or involves risk. One form will be used per event or problem.

Table 4.1: Unanticipated Problems Involving Risk to Patients or Others			
	Phase I	Phase II	Total
UPIRTSO 1 (number)			
UPIRTSO 2 (number)			
UPIRTSO 3 (number)			
Overall UPIRTSOs Reported			

Table 4.2: Risk/ Mitigation Measures	
Identified Risk	Mitigation Measures

Insert Safety Analysis Here

Section 5.0: Results

Results: The principal safety and effectiveness results from patients in the Nu-V3 study are provided below. The primary safety analysis was based on all patients registered and included all reported UPIRTSO events. The primary safety endpoint included imputation for missing clinical outcomes data using the logistic regression method. The imputation model included baseline characteristics including age, sex/gender, marital status, primary language spoken, race/ethnicity, education history, and veteran status.

Primary Safety Endpoint:

Insert Primary Safety Endpoint Statistical Analysis

Insert Primary Safety Endpoint Statistical Table

Primary Effectiveness Endpoint:

Insert Primary Effectiveness Endpoint Statistical Analysis

Insert Primary Effectiveness Endpoint Statistical Table- 8 weeks

Secondary Effectiveness Endpoint:

Insert Primary Effectiveness Endpoint Statistical Analysis

Insert Primary Effectiveness Endpoint Statistical Table: 4, 8, 12 weeks

Sub-Analyses:

Insert Sub-Analyses Statistical Analysis

Insert Sub-Analyses Statistical Tables

Special Controls:

Insert Special Control Section Here

Benefit/Risk Determination:

Insert Benefit/Risk Section Here

Section 5.0: Administrative Information

Administrative information consists of the study results point of contact and any agreement between the sponsor and principal investigator (PI) restricting the ability of the PI to discuss the results after the completion of the study.

Conclusion:

The de novo for Nu-V3 is _____ and the device is classified under the following:

Product Code:

Device Type:

Class:

Regulation:

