## 8.0 STUDY ENDPOINT and DATA ANALYSIS

### 8.1 Primary Endpoints: Primary endpoints consisted of the following:

Safety: The primary safety endpoint is the occurrence of reported unanticipated problems involving risk to subjects or others (“UPIRTSOs”). These UPIRTSOs are defined as those problems which alter the risks to subjects or others. This includes any study suspensions or holds. The primary safety endpoint analyses will be based on a risk-benefit conclusion.

Effectiveness: The primary effectiveness endpoints are an overall change in median reported symptoms of pain, anxiety, depression, and/or sleeplessness via numeric rating scales at 8 weeks. This primary effectiveness is measured by median reported symptom changes in pain, anxiety, depression, and/or sleeplessness for respective stratified populations via the following validated tools: Pain - Pain Intensity and Interference (PEG\_Scale), Anxiety - Generalized Anxiety Disorder 7-item (GAD-7) scale, Depression - Patient Health Questionnaire (PHQ-9), Sleeplessness - PROMIS short form 4a, and overall improvement of quality of life (QOL) - Patient’s Global Impression of Change (PGIC).

The hypothesis-driven criterion of effectiveness is to show that there is a statistically significant reduction in the median reported pain, anxiety, depression, and/or sleeplessness levels of patients using the Nu-V3 device. The second criterion is intended to show that there is a statistically significant improvement in reported quality of life and perceived treatment benefit, secondary to overall reported symptom reductions of pain, anxiety, depression, and/or sleeplessness.

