### 8.2 Secondary Endpoints: Secondary endpoints consisted of the following:

Effectiveness: The secondary effectiveness endpoint is an overall change in median reported symptoms of pain, anxiety, depression, and/or sleeplessness for respective stratified populations via numeric rating scales at 4, 8, and 12 weeks. This is measured via the following validated tools: Pain – Pain Intensity and Interference (PEG\_Scale), Anxiety - Generalized Anxiety Disorder 7-item (GAD-7) scale, Depression - Patient Health Questionnaire (PHQ-9), Sleeplessness - PROMIS short form 4a, and overall improvement of quality of life- Patient’s Global Impression of Change (PGIC).

The patient’s perceived treatment benefit and device comfort information will be captured via the non-validated tool, Perceived Treatment Benefit Form (PTB-7). This effectiveness tool will measure median levels of reported perceived treatment benefit and device comfort.

The hypothesis-driven criterion is to show that there is a statistically significant reduction in the median reported pain, anxiety, depression, and/or sleeplessness levels of patients using the Nu-V3 device at weeks 4, 8, and 12. The second criterion is intended to show that there is a statistically significant improvement in reported quality of life and perceived treatment benefit secondary to overall reported symptom reduction of pain, anxiety, depression, and/or sleeplessness at weeks 4, 8, and 12.

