### 8.3 Sub-Analyses: Sub-Analyses Consist of the following:

The sub-analyses endpoints consist of the mean number of weeks that pain, anxiety, depression, and sleeplessness response are achieved and sustained, without utilization of another device, during the 8-week intervention. In addition, study sub-analyses also include the mean number of weeks to initial benefit from Nu-V3 device use, and the mean medication dosage reduction of short acting pain, anxiolytics, and/or insomnia. The device's comfort-of-use, and patient's perceived treatment benefit will also be captured for sub-analyses.

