**Form PTB-7: Patient's Perceived Treatment Benefit**

[figure not shown]
For *initial assessment* of all symptoms, please rate your average symptom score prior to any treatment (i.e. over the last 30 days)

For any assessment *after treatment has been initiated*, please rate your global average symptom score since your last treatment

1. On a scale of 0-100%, how much benefit do you feel you have received from the Nu-V3 treatment in helping your symptoms?

2. How comfortable was the Nu-V3 device to wear?

3. Have you had any major discomfort from the device that has necessitated you to adjust the device placement?

\_\_\_\_ Yes  
\_\_\_\_ No

[figure not shown]
Subject ID \_\_\_\_\_ Date (dd/mmm/yyyy): \_\_\_\_/\_\_\_\_/\_\_\_\_

For *initial assessment* of all symptoms, please rate your average symptom score prior to any treatment (i.e. over the last 30 days)

[figure not shown]
For any assessment *after treatment has been initiated*, please rate your global average symptom score since your last treatment

4. Please rate your pain, anxiety, depression, and/or sleeplessness on a 0-10 scale:

[figure not shown]
Pain Level:

Anxiety Level:

Depression Level:

Sleeplessness Level:

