Primary Endpoints: Primary endpoints consisted of the following:

1. **Safety:** The primary safety endpoint was the occurrence of reported unanticipated problems involving risk to subjects or others (“UPIRTSOs”). These UPIRTSOs are defined as those problems which alter the risks to subjects or others. This includes any study suspensions or holds. The primary safety endpoint analyses were based on a risk-benefit conclusion.
2. **Effectiveness:** The primary effectiveness endpoints were overall reduction in median reported symptoms of pain, anxiety, depression, and/or sleeplessness via numeric rating scales at 8 weeks. This primary effectiveness is measured by median reported symptom reductions in pain, anxiety, depression, and/or sleeplessness via the following validated tools: Pain intensity and interference- PEG Scale, Anxiety- Generalized Anxiety Disorder 7-item (GAD-7) scale, Depression- Patient Health Questionnaire (PHQ-9), Sleeplessness- PROMIS short form 4a, and overall improvement of quality of life (QOL) - Patient’s Global Impression of Change (PGIC).

The patient’s perceived treatment benefit and device comfort information, will be captured via the non-validated tool, Perceived Treatment Benefit Form (PTB-7). This effectiveness tool will measure median levels of reported perceived treatment benefit and device comfort.

The hypothesis-driven criterion of effectiveness was to show that there was a statistically significant reduction in the median reported pain, anxiety, depression, and/or sleeplessness levels of patients using the Nu-V3 device. The second criterion was intended to show that there was a statistically significant improvement in reported quality of life and perceived treatment benefit secondary to overall reported symptom reduction of pain, anxiety, depression, and/or sleeplessness.

Secondary Endpoints: Secondary endpoints consisted of the following:

1. **Effectiveness:** The secondary effectiveness endpoint was overall reduction in median reported symptoms of pain, anxiety, depression, and/or sleeplessness via numeric rating scales at 4, 8, and 12 weeks. This was measured via the following validated tools: Pain intensity and interference- PEG Scale, Anxiety- Generalized Anxiety Disorder 7-item (GAD-7) scale, Depression- Patient Health Questionnaire (PHQ-9), Sleeplessness- PROMIS short form 4a, and overall improvement of quality of life- Patient’s Global Impression of Change (PGIC).

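### The non-validated PTB-7 benefit rating is primary in the SAP and secondary in the protocol, and the second primary criterion seeks an improvement that its 0-100% item cannot properly measure

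*SAP*

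**What the plan says.** **Where the form is named.** Protocol 8.1 lists five primary tools: PEG, GAD-7, PHQ-9, PROMIS 4a and PGIC. PTB-7 is not one of them. It enters in 8.2, Secondary Endpoints, where perceived benefit and device comfort are "captured via the non-validated tool, Perceived Treatment Benefit Form (PTB-7"). Section 8.3 then lists the same concept a second time: "perceived treatment benefit will also be captured for sub-analyses".

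The SAP carries the PTB-7 paragraph under Primary Endpoints, item 2 (Effectiveness): the information "will be captured via the non-validated tool, Perceived Treatment Benefit Form (PTB-7"), followed by "This effectiveness tool will measure median levels of reported perceived treatment benefit and device comfort". The paragraph does not appear under the SAP's Secondary Endpoints, item 1, but perceived benefit is again among the sub-analyses (Secondary Endpoints, item 2).

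**What the criterion says.** The second primary criterion in protocol 8.1 is intended to show a "statistically significant improvement in reported quality of life and perceived treatment benefit, secondary to overall reported symptom reductions". The SAP's version is nearly word for word the same: "statistically significant improvement in reported quality of life and perceived treatment benefit secondary to overall reported symptom reduction". Both documents repeat it under the secondary endpoint for weeks 4, 8 and 12.

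**What the form asks.** PTB-7 item 1 (protocol Appendix 11) asks, on a 0-100% scale, "how much benefit do you feel you have received from the Nu-V3 treatment in helping your symptoms". Item 2 concerns comfort, item 3 major discomfort, and item 4 rates the four symptoms on 0-10.

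**The concern.** Perceived benefit sits at three levels across the two documents: primary, secondary and sub-analysis. The SAP describes this as the pivotal study supporting a De Novo request. If the level is not settled before analysis, a favourable result could be presented as primary and an unfavourable one as a sub-analysis.

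The wording of the criterion is a second problem. Improvement needs a starting point. Before the device is worn there is no benefit from it to rate, so a pre-device answer to item 1 is either meaningless or zero by construction. Zero is also the lowest answer, so measured from zero the rating can only stay or rise. A significance test built on that would say little about whether the device works, especially in a single-arm, open-label study.

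**Working it through.** There is no stated figure to reproduce: neither document gives a test, reference value, alpha or power basis for this measure. The check is therefore a comparison of texts, followed by a labelled illustration.

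**1. Role of PTB-7 or perceived benefit**

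| Place | Protocol | SAP |
|---|---|---|
| Named as a tool under Primary | No (8.1) | Yes (Primary, item 2) |
| Perceived benefit in second primary criterion | Yes (8.1) | Yes |
| Named as a tool under Secondary | Yes (8.2) | No |
| Perceived benefit in second secondary criterion | Yes (8.2) | Yes |
| Listed as a sub-analysis | Yes (8.3) | Yes |

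The documents conflict on where the tool belongs. The protocol also has an internal gap: its primary criterion uses a concept that none of the 8.1 tools is assigned to measure.

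**2. Is there a usable baseline?** The ePRO packet, which includes PTB-7, is marked at Week 1 (protocol 4.1 and the matching SAP table). The form's instruction for the initial assessment refers to symptom scores before treatment. That gives item 4 a baseline, but not item 1.

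**3. Illustration of what a test on item 1 could do**

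Inputs:
- Planned Phase I size: 50-100 (protocol 4.0).
- Two-sided alpha 0.05: an assumption. The only mention is an example in the generic checklist text of SAP Section 3.0.
- Reference value 0: an assumption.
- Zeros dropped: an assumption.

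Every non-zero rating is then positive. For k non-zero ratings the exact two-sided sign or signed-rank p-value is 2 × 0.5^k:
- k = 5: 2 × 0.03125 = 0.0625
- k = 6: 2 × 0.015625 = 0.03125

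Six patients reporting any benefit are enough, whether 44 of 50 or 94 of 100 report 0%. The chance of at least six non-zero ratings, by assumed share reporting any benefit, is:

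| Share above 0% | N = 50 | N = 100 |
|---|---|---|
| 10% | 38% | 94% |
| 20% | 95% | over 99.9% |

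**4. Sensitivity to the treatment of zeros.** Take 6 of 50 non-zero. Splitting the 44 zeros evenly gives 6 + 22 = 28 positives of 50, and a two-sided sign test gives p of about 0.48. The median is 0. The small p-value therefore comes from dropping the zeros.

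**5. Effect of the floor.** In 2,000 simulated trials at each size, true change was symmetric about zero with an assumed SD of 25 points. With changes cut off at 0 and zeros dropped, the signed-rank test rejected in 100% of runs at N = 50 and at N = 100. Without the cut-off it rejected in 4.65% and 5.1%.

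**The case against.** Several points on the other side are sound.

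- **The criterion does not differ.** A reader might infer that the documents disagree on what has to succeed. They do not: the second criterion is worded alike in both. What differs is the level at which the tool is named.
- **Nothing is formally required.** Both texts say what the criterion is intended to show, and neither says whether both criteria must be met. Within the second criterion, quality of life and perceived benefit are joined by and. On that reading an easily met component leaves PGIC to decide and adds no false-positive risk of its own.
- **The SAP does not build an analysis on PTB-7.** Its primary effectiveness sentence rests on the five named tools, and PTB-7 is said to yield median levels. Section 3.0 has outcome templates for pain, anxiety, depression, sleeplessness, quality of life (PGIC) and medication dosage, but none for PTB-7.
- **The form as a whole can record harm.** Item 3 captures major discomfort, and item 4 can show worsening symptoms from a pre-treatment rating.
- **The illustration is conditional.** Another handling of zeros reverses its result. A comparison between two visits on treatment could also fall, although none is specified.

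These points narrow the concern. They do not remove the conflict over placement, nor the fact that improvement in item 1 has no defined starting point and no room below zero.

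**Conclusion.** The concern holds in a limited form, and the matter should be fixed. The SAP gives primary standing to a form that it calls non-validated and that the protocol names only as secondary. Both documents then seek a statistically significant improvement in a rating that has no meaningful pre-device value and cannot fall below zero. The last two points concern item 1 only.

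It would go too far to say that the primary result depends on PTB-7, or that its test is passed almost automatically. The first criterion, symptom reduction, does not involve it. The p-value of 0.031 with six non-zero ratings depends on an assumed test against 0, dropped zeros and an assumed alpha of 0.05; with zeros split evenly the same 6 of 50 gives about 0.48. What does not depend on these assumptions is that, measured from zero, the rating can only favour the device.

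**What to change.** - **SAP, Primary Endpoints:** move the PTB-7 paragraph to Secondary Endpoints, to match protocol 8.2.
- **Protocol 8.1 and SAP, second primary criterion:** strike the reference to perceived treatment benefit.
- **Sub-analyses:** remove the duplicate entry from both protocol 8.3 and the SAP list, so that the measure stands at one level only. Removing it from one document alone would create a new mismatch.
- **Reporting:** present item 1 descriptively (median, quartiles, percent reporting 0%), not as a test of improvement.

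Whether the same words also leave the secondary criterion is more a matter of preference; if they stay, they should be read in line with the descriptive reporting.

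The cost is wording only. Data collection and the five tools in 8.1 are unchanged, and the sponsor gives up a formal significance claim on perceived benefit.

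One limit remains. The second criterion would then rest on PGIC, whose lowest score combines no change with worsening (Appendix 11). This fix does not by itself make that criterion able to show harm.

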## 5.0 DATA COLLECTION AND RETENTION

The study endpoints data will be collected from each participant's study questionnaires. The data will be collected electronically via the patient's own device, and uploaded to an electronic data capture system. Only patient data from the stratified indication(s) will be used for analysis of symptom response. The data will be used to demonstrate that the Nu-V3 device provides participants with relief of the symptoms of pain, depression, anxiety and/or sleeplessness. The data analysis will include comparative data for each participant's questionnaire prior to beginning treatment with the Nu-V3 device, the participant's weekly questionnaires during

treatment and the questionnaire completed at the end of the treatment with the Nu-V3 device.

Interim analyses of available data will be regularly submitted to the FDA for review.

The Principal Investigator at each site will be responsible for recording, collecting, and storing the research participant's study data. The written records must be stored in a secure location. Only the Principal Investigator or designated study staff will have access to the study records and all electronic files will be password protected. The Principal Investigator will also maintain adequate records for the study including:

- all correspondence with the IRB and Sponsor
- other pertinent data related to the study

All records are to be retained by the Principal Investigator for a period of seven (7) years following the closure of the study. Following study closure, the Principal Investigator shall inform Nu-Life of the location of study records and storage changes (i.e. the Principal Investigator leaves the institution where the study was conducted). In such cases, the study records may be transferred to another institution, investigator, or to Nu-Life upon written agreement between the Principal Investigator and Nu-Life.

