- Participants with any changes to Pain/Anxiety/Depression/Sleeplessness medications within last 60 days (participants that do not meet this medication change washout period may be delayed until 60-day period is met)
- Participants that are currently under adjudication process for disability support, VA or other

Accountability: Patients were exited from the study upon completing the final protocol-required questionnaires. In some cases, patients prematurely exited or withdrew from the study for the following reasons, including but not limited to:

- Not eligible for treatment (including patients who may have signed informed consent and been enrolled).
- Patient experienced a SAE or UPIRTSO.
- Voluntary withdrawal- the patient voluntarily chose not to participate further in the study.

- Lost to follow-up (LTFU) – the patient was more than 10 days late to a study visit and three documented attempts to contact the patient were unsuccessful. A patient who missed a study visit but attended subsequent visit (if required) was no longer considered lost to follow-up. A missed visit was considered a protocol deviation and the deviation was documented and reported.
- Physician decision – in the physician’s opinion, it was not in the best interest of the patient to continue study participation.

The tables below summarize patients who exited the study early, as well as those who completed all study participation as per protocol.

Table 1: Study Exit Summary- Early Exit (<8 weeks)			
	Phase I	Phase II	Total Enrolled
Voluntary Withdrawal			
Lost to Follow-Up			
Physician’s Decision			
SAE / UPIRTSO			
Other			
Overall “exited” Patients			

Table 2: Study Exit Summary (≥ 8 weeks)			
	Phase I	Phase II	Total Enrolled
Completion of Study as Planned			
Voluntary Withdrawal			
Lost to Follow-Up			
Physician’s Decision			
SAE / UPIRTSO			
Other			
Overall “exited” Patients			

Insert Study Exit Analysis Here

Section 1.0: Participant Flow

ClinicalTrials.gov

A service of the National Institutes of Health

Edited: 19 August 2014

Participant Flow Data Preparation Checklist

Overview: A tabular summary of the participants' progression through each stage of a study by group. Use this checklist with the [Participant Flow Template](#)^Δ and [Results Data Element Definitions](#).

	Information to have available for Participant Flow	Term

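### Effectiveness, unlike safety, has no all-treated population and no rule for a missing Week 8 score, and nothing says that a patient who stops the device keeps reporting

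*SAP*

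**What the plan says.** **Early exit.** SAP Accountability states: "In some cases, patients prematurely exited or withdrew from the study for the following reasons". The reasons listed include "Patient experienced a SAE or UPIRTSO", loss to follow-up, physician decision, and voluntary withdrawal, where "the patient voluntarily chose not to participate further in the study". Ineligibility discovered after enrolment is also on the list. SAP Table 1 counts exits before 8 weeks by reason and does nothing further with them.

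**Data collection.** The assessment tables in protocol section 4.1 and in the SAP list the patient questionnaires (ePROs) by study week. They are completed on the patient's own phone and continue into Weeks 9-12, when no device is worn. Neither table has an early-termination column or a note on what happens after exit.

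**Effectiveness.** Protocol section 8.1 sets the primary endpoint as a change in median symptoms "via numeric rating scales at 8 weeks", "for respective stratified populations via the following validated tools". Protocol section 5.0 adds: "Only patient data from the stratified indication(s) will be used for analysis of symptom response". In the SAP results section, the primary effectiveness analysis is a placeholder. The analysis-population field is blank in the pain, anxiety, depression, sleeplessness and quality-of-life templates.

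**Safety.** The same SAP section is specific here: "The primary safety analysis was based on all patients registered and included all reported UPIRTSO events", and "The primary safety endpoint included imputation for missing clinical outcomes data using the logistic regression method". It also names the baseline variables in the imputation model.

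**The concern.** This is a single open-label arm, so change from baseline is the whole evidence of benefit. If a patient leaves before Week 8 and no score is collected or imputed, that patient drops out of the median. Were exits concentrated among poor responders, the remaining group would look better than the treated group even with a device that does nothing.

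The second problem is the pairing with safety. Safety covers everyone registered. The benefit-risk determination could then set harm in all registered patients against benefit in those who stayed.

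Timing matters more than wording. A missing-data method can be written later, though less credibly once interim data have been seen. A Week 8 score that was never collected cannot be recovered.

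**Working it through.** The plan gives no exit rate, standard deviation, test, significance level or stratum size, so there is no figure of its own to reproduce. The check is a comparison of text, then an illustration.

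**Text, side by side**

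| Item | Safety | Effectiveness |
|---|---|---|
| Population | All registered patients | Baseline symptom stratum; no statement on those who exit |
| Missing outcome | Logistic-regression imputation | None; placeholder |
| Reporting after device stop or SAE | Not applicable | Not stated |

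**Illustration: inputs**

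- From the documents: 50-100 patients in Phase I; endpoint at Week 8; a single arm.
- Assumed: n = 50 in the stratum, normal change scores, no true change, and a two-sided 0.05 signed-rank test on completers (2.5% in the favourable direction).

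**Model.** Improvement x ~ N(0,1), in SD units. Exit score e = ρx + √(1−ρ²)·noise. The k patients with the lowest e leave, so ρ > 0 means poor responders tend to leave and ρ < 0 means improvers do. With m = 50 − k completers, Z = (W⁺ − m(m+1)/4) / √(m(m+1)(2m+1)/24), and false benefit is Z > 1.96.

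Example for k = 5, m = 45: the mean of W⁺ is 45·46/4 = 517.5 and its SD is √(45·46·91/24) = √7848.75 = 88.6. False benefit therefore needs W⁺ above 517.5 + 1.96·88.6 ≈ 691.

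**Results** (40,000 simulated trials per cell, % with false benefit)

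| Exits of 50 | ρ = 0.5 | ρ = 0.3 | ρ = 0 | ρ = −0.5 |
|---|---|---|---|---|
| 2 (4%) | 4.6 | 3.7 | 2.5 | 1.3 |
| 5 (10%) | 9.2 | 5.6 | 2.5 | 0.7 |
| 10 (20%) | 19.3 | 9.4 | 2.4 | 0.2 |

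At ρ = 0.5 the completers' median is shifted by 0.04, 0.09 and 0.16 SD at 2, 5 and 10 exits. At ρ = −0.5 the shift is of the same size in the other direction.

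As a limit, if exactly the worst 10% or 20% leave, the remaining median sits at percentile 1 − (1 − 0.1)/2 = 0.55 or 1 − (1 − 0.2)/2 = 0.60 of the full group. That is an apparent gain of 0.13 or 0.25 SD.

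**Effect of continued collection** (n = 50, ρ = 0.5, exits 2/5/10). If a random quarter of those who exit still give a Week 8 score, false benefit is 4.0/6.8/12.4%; if half do, 3.4/5.0/7.5%.

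**The case against.** Several points on the other side stand.

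- **No completers-only analysis is written.** A reader might infer that the plan has chosen one. It has not; this is only the default when scores are neither collected nor imputed. The protocol and SAP do mention an end-of-treatment questionnaire, which might be taken to supply a last score for early exits. It is not written as a missing-score rule, and the endpoint is fixed at Week 8.
- **Stopping the device need not end participation.** A reader might infer that an SAE forces a patient out. The SAP lists SAEs among reasons for exits that occurred and does not mandate exit. The Unanticipated Problem Form in Appendix 7 allows for no action on the device, and for interruption followed by restart. The schedules place questionnaires by week whether or not a device is worn, and the SAP ties normal exit to completing the final questionnaires. Part of the fix is therefore clarification. Protocol section 4.2 does not settle the matter, since its text on removal covers accidental detachment.
- **Silence is weak evidence.** A visit schedule would not normally show data after exit. The consent form, process maps and CONSORT figure, where exit handling might appear, were not available, and nothing is held against the plan on their account.
- **The gap is part of a larger one.** The effectiveness analysis also lacks a test and a significance level, so the contrast with safety may not be deliberate. Even so, no effectiveness rule exists, and this gap differs from the others in that the lost data cannot be restored.
- **Bias need not favour the device.** Patients may leave because they improved, which works against it.

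**Conclusion.** The point holds as an omission worth repairing. On the available text, the Week 8 median would by default describe those who remained, while safety describes everyone registered. A reader might infer that the result is necessarily biased towards the device; the documents do not support that. The bias favours the device if poor responders leave, goes against it if improvers leave, and is nil if exit is unrelated to outcome.

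Its size is unknown. About 5/9/19% false benefit at 2/5/10 exits rests on an assumed correlation of 0.5, a stratum of 50 and a signed-rank test; reversing the correlation gives about 1.3/0.7/0.2%. No exit rate in the documents supports the higher figures, and with only one or two exits the effect is small. Confidence is medium. The change is recommended because it is cheap now and cannot be made after the data are lost.

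**What to change.** 1. In SAP Accountability, with a matching sentence in the protocol, state that an SAE, a UPIRTSO or stopping the device does not by itself end participation. Unless consent is withdrawn, the patient continues the scheduled phone questionnaires through Week 12.
2. Define the Week 8 effectiveness set as all patients in the stratum who had a device placed, and say whether those later found ineligible are included.
3. Choose one method for the remaining missing scores, suited to a median endpoint, and fix it before data are reviewed, which means before the Week 4 interim analysis. Report completers-only and missing-as-not-improved as sensitivity analyses.

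**Choice of method.** Multiple imputation from baseline and weekly scores is a candidate. It was tried here only with a t-test on mean change, assuming a correlation of 0.7 between earlier and Week 8 change. At n = 50, ρ = 0.5 and 2/5/10 exits, false benefit was 2.9/2.4/2.6% when exit depended on the earlier score, but 3.4/5.8/9.6% when it depended on the unseen Week 8 change. It would need adapting to the median, and it reduces rather than removes the problem.

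Missing-as-not-improved should stay a sensitivity analysis because it loses power. With a true 0.5 SD benefit (n = 50, ρ = 0.5), a sign test requiring 33 of 50 improved has power 74% with no exits and 69/55/23% with 2/5/10.

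**Cost.** Wording in two documents and a few minutes a week for patients off the device. No visits are added, since off-device phone questionnaires are already scheduled in Weeks 9-12. The median may be less favourable, and patients who withdraw consent or are lost are not recovered.
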